3 STUDY DESIGN

The study is a multicenter, randomized, double-blind, placebo-controlled, parallel group, add-on pilot trial in patients taking riluzole. Patients diagnosed with ALS who meet the study's inclusion and exclusion criteria and sign the Informed Consent Form (ICF) will be enrolled. There will be two groups making up a total of 142 subjects: Group A (71 subjects) and Group B (71 subjects). Subjects will be randomly assigned to receive treatment with either RNS60 or placebo while concomitantly taking riluzole (50 mg twice a day). RNS60 or placebo will be administered intravenously once a week as well as inhaled via nebulization every morning (6 days a week on non-infusion days) for 24 weeks. All visit windows (± 1 or $+ 4$ days according to study procedure) are consecutive calendar days and are calculated from the day the participant starts study treatment (the day of the Randomization-Baseline Visit).

Blood samples will be collected five times for enrolled subjects to measure biomarkers. The first blood sample collection will be at baseline before the first infusion dose. Safety and efficacy will be assessed by way of physical exam, vital signs and AEs. Changes in disability and quality of life will be assessed using the ALSFRS-R scale, FVC and ALSAQ-40 scale. The overall treatment duration will be 24 weeks. Each subject will be followed up for a maximum period of 48 weeks (24-week treatment + 24-week follow up) or until death or tracheotomy, whichever occurs first.

4 STUDY POPULATION

4.1 Disease definition

[....]

Included in the study may be cases of bulbar-onset and spinal-onset ALS. Cases with only bulbar signs or symptoms for the first three months from onset, with spinal symptoms or signs occurring later, are considered bulbar onset ALS. Cases in which any spinal symptoms or signs appeared in the first three months are considered spinal onset ALS. Bulbar onset and spinal onset ALS will be considered separately at the analysis stage.

Patients not fulfilling the diagnostic criteria as indicated in the protocol cannot be enrolled.

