2.4 Secondary Endpoints

1. The mean change in the proportion of T-reg (measured via FOXP3 and CD25 mRNA); the mean change over time in the plasma concentrations of Cyp-A, 3-NT, Actin-NT, MCP-1, IL-17 during the follow up period (from 24 to 48 weeks);
2. The cumulative proportion of subjects becoming no longer self-sufficient at 4, 12, 24, 36 and 48 weeks in the two treatment arms (defined as those scoring 2 or lower on at least one of the ALSFRS-R items for swallowing, cutting food and handling utensils, or walking);
3. The mean change of ALSFRS-R total score in the two treatment arms during the treatment and follow up period;
4. The cumulative proportion of deaths or tracheostomies in the two treatment arms during the entire study including follow-up;
5. The mean change of FVC score in the two treatment arms during the treatment and follow up period;
6. The total number of subjects in the two treatment arms experiencing at least one AE leading to treatment discontinuation at 4, 12 and 24 weeks;
7. The mean number of AEs per treatment arm at 4, 12, 24 and 48 weeks;

8. The mean change of ALSAQ-40 score measuring quality of life at the completion of the treatment and follow up period.

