4.2 Inclusion Criteria

- 1) Age 18 through 80 years inclusive;

- 2) Geographically accessible to the site and able to come to the site center once a week for 24 weeks;
- 3) “Definite” or “Probable” or “Probable laboratory-supported” ALS diagnosis according to the revised El Escorial criteria;
- 4) Disease duration 6 to 24 months from symptom onset to study entry;
- 5) Self sufficiency: Satisfactory bulbar and spinal function (score 3+ on the ALSFRS-R for swallowing, cutting food and handling utensils, and walking);
- 6) Satisfactory respiratory function (FVC \geq 80% of predicted);
- 7) Documented progression of symptoms in the last three months as measured by the ALSFRS-R scale (decrease of at least one point);
- 8) Ability to understand and comply with the study requirements;
- 9) Ability to give written informed consent personally or, as an alternative, via a legally authorized representative;
- 10) Treatment with riluzole 50 mg twice/day for at least 1 month prior to screening visit;

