11 STATISTICS

11.1 Sample Size Calculation

We analyzed preliminary data on Cyp-A which showed an increase of 0.27 over six months (Nardo, G. et al. 2011). With 142 patients enrolled, we will have 80% power to detect a 44% decrease in the rate of progression in Cyp-A at a two sided $p=0.05$ significance level. This assumes a drop-out rate of 1.75% per month (10% over the study). The calculation is based on the method shown in (<http://hedwig.mgh.harvard.edu/biostatistics/node/42>). For the other biomarkers we only had data on the between patient variation and not on the within patient variation which could be used for calculating sample size for the proposed study. Usually the within patient variation is less than the between patient variation, so power calculated using the between patient variation is conservative. The T-reg values were assessed in slowly progressing vs. rapidly progressing ALS43 and the estimated difference was used as the difference expected to slow the progression of the disease in patients receiving RNS60. A total of 128 patients is needed to detect a difference in means of 0.25 units between the two treatment arms at 24 weeks with a standard deviation (SD) of 0.5. Similar assumptions were made for the other biomarkers for which, except for Actin-NT (that would require 1542 patients), numbers range from 8 to 68 (Nardo, G. et al. 2009; Nardo, G. et al. 2011; Henkel, J. et al. 2013; Chiò A. et al., 2011):

- MCP-1: a total of 16 patients is needed to detect a difference in means of 220 units between the two treatment arms at 24 weeks with a standard deviation (SD) of 140;
- Actin-NT: a total of 1542 patients is needed to detect a difference in means of 0.1 units between the two treatment arms at 24 weeks with a standard deviation (SD) of 0.7;
- 3-NT: a total of 24 patients is needed to detect a difference in means of 50 units between the two treatment arms at 24 weeks with a standard deviation (SD) of 40;
- Cyp-A: a total of 68 patients is needed to detect a difference in means of 1.4 units between the two treatment arms at 24 weeks with a standard deviation (SD) of 2.0.

For ALSFRS-R, the software <http://hedwig.mgh.harvard.edu/biostatistics/node/42> shows the variance parameters which are from the Celebrex Study.

The variance of the random effects is the matrix 31.8 (intercept), 0 .6687 (slope) with a covariance of 0.8527. The error has a variance of 2.7.

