With 142 patients enrolled, we will have 80% power to detect a 43% decrease in the rate of progression in ALSFRS over 6 months, at a two sided $p=0.05$ significance level. The study is also powered (in this case $p=0.05$ two sided) to show an absolute 25% reduction in the proportion of patients becoming non self-sufficient at 24 weeks, using a validated outcome measure with strong clinical significance (Marin, B. et al. 2015). In two studies from our group (Beghi, E. et al 2013; Chiò, A. et al. 2010) the average proportion of patients becoming non self-sufficient after 24 weeks in the placebo arm was 85%.

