11.2 Statistical Analysis Plan

The study will use a modified intent to treat approach with all patients included who took at least one dose of the study medication or placebo. The primary analysis, described below, is valid as long as the probability of non-observation of a data point is independent of the value that would have been observed conditional on the previous observed data. In the case of ALSFRS this method has been shown to be robust (Ref <http://www.ncbi.nlm.nih.gov/pubmed/22987690>). Separate analyses will be performed in: 1. All randomized subjects receiving at least one dose of study medication (Intention-to-treat population); 2. Study completers: subjects completing the 12-month follow-up; 3. Study completers and compliers: subjects completing the 12-month follow-up and taking at least 75% of assigned dose. 4. All randomized subjects excluding protocol deviations (Per protocol, PP population). Descriptive statistics will be performed comparing the two treatment groups and safety of RNS60 and placebo. Continuous variables will be described using mean and standard deviation or median and interquartile range; categorical variables will be described as counts and percentages.

Biomarkers analysis:

The primary analysis will be a repeated measures analysis of variance (ANOVA) with a treatment variable that is the same for all treatments at baseline and then differs at later observation times. We will use an unstructured variance covariance matrix. The contrast of interest will depend on the outcome. Note that this is more general than a random effects model in situations where the observation times are fixed. For biomarkers that progress over time such as Cyp-A, the primary analysis will compare the rate of change in the biomarker over time in the placebo and active treatment groups. In biomarkers that do not progress but rather are elevated in patients, the primary analysis will be a comparison in the treatment effect. Both of these analyses are contrasts in a repeated measures ANOVA, the former by treatment \times time, and the latter being treatment \times (time>0). Each biomarker will be analyzed separately.

Efficacy analysis:

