The numerical change of FVC, ALSFRS-R and ALSAQ-40 during the treatment and follow-up period will be assessed using repeated measures ANOVA, with an unspecified variance covariance matrix. The hypothesis will be tested using the time*treatment interaction which measures differences in the slope of the ALSFRS-R. Survival (time to death or tracheostomy) and time to functional disability (i.e., to reach a non self-supporting status or death or tracheostomy) will be assessed using actuarial methods with death and non-self supporting status as end-points. Survival will be described with the Kaplan-Meier method. Differences between the two treatment groups will be compared using the log-rank test. The statistical significance will be set at the 0.05 level for a two-tailed test.

The repeated measures ANOVA will use all available data, using Maximum Likelihood methods as suggested by (<http://www.nap.edu/read/12955/chapter/1>).

Safety analysis will be performed in all subjects receiving at least one dose of the experimental drug. All AEs, SAEs and AEs leading to treatment discontinuation will be recorded, listed and compared in the two treatment arms at any follow-up visit and at the end of the study. The number of patients reporting at least one AE or SAE will be compared between the treatment arms using the fisher exact test. The total number of AE and SAE will be compared between the treatment arms using a poisson model. MedDRA code system will be used for all recorded AE/SAE.

Given the exploratory value of this study, multiple comparison adjustments for Type I errors will not be considered as a more conservative significance level would lead to miss any potential treatment effect. Furthermore, if there is a suggestive benefit ($p<0.1$) in the clinical measures and several of the biomarkers, this will be considered sufficient evidence for further study.

If at the end of the patient enrolment period less than 50% of patients are enrolled, an interim-analysis will be performed to decide whether or not to continue the trial.

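### Section 4.1 says onset type will be considered separately at analysis, but the models and log-rank tests in 11.2 do not use it; naming it there is a cheap, minor improvement

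*Combined protocol and SAP*

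**What the plan says.** Section 4.1 admits both onset types, separates them by a three-month rule, and commits: "Bulbar onset and spinal onset ALS will be considered separately at the analysis stage". It does not say how.

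Section 11.2 is where a method would be expected.
- **Analysis sets.** "Separate analyses will be performed in: 1. All randomized subjects receiving at least one dose of study medication", followed by completers, completers who complied, and a per-protocol set. None is defined by onset.
- **Biomarkers.** "The primary analysis will be a repeated measures analysis of variance (ANOVA) with a treatment variable"; the contrasts are treatment by time, or treatment by an indicator for time after baseline.
- **FVC, ALSFRS-R and ALSAQ-40.** "The hypothesis will be tested using the time*treatment interaction which measures differences in the slope of the ALSFRS-R".
- **Survival and time to functional disability.** Kaplan-Meier description and a log-rank comparison, with no strata named.

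The part of 11.2 that sets out these analyses carries no mark of removed text. Section 11.1 sizes the whole-arm comparison only, including an "absolute 25% reduction in the proportion of patients becoming non self-sufficient at 24 weeks" from a placebo figure of 85%.

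**The concern.** A commitment made in one section is not carried out in the section that specifies the analysis. Considering the groups separately could mean stratified tests, covariate adjustment, descriptive subgroup estimates, or separate hypothesis tests in each group. Section 11.2 makes no multiplicity adjustment and treats p<0.1 on the clinical measures and several biomarkers as enough for further study. If the choice is left until data are seen, within-onset results could be read selectively.

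The second stake is precision. If onset is prognostic, an unstratified log-rank test loses some power that a stratified one keeps, and a slope model without an onset-by-time term leaves explainable variation in the error.

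**Working it through.** **1. Reproducing the plan's figures.**
- T-reg (11.1): difference 0.25, SD 0.5, so d = 0.5. A two-sample t-test at two-sided 0.05 and 80% power needs 64 per arm, 128 in total, as stated. With 71 per arm, power is 84.1%.
- Self-sufficiency (11.1): 85% v 60%, 71 per arm. Power = Φ[(0.25√71 − 1.96√(2 × 0.725 × 0.275)) / √(0.85 × 0.15 + 0.60 × 0.40)] = Φ[(2.107 − 1.238) / 0.606] = Φ(1.43) = 92.4%.

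Neither calculation contains an onset input, and both support the whole-sample comparison.

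**2. Self-sufficiency log-rank test, unstratified v stratified by onset.** From the documents: 71 per arm, 85% v 60% at 24 weeks, drop-out 1.75% per month, assessments at weeks 4, 12, 24, 36 and 48. Assumed: bulbar share s = 30% (range 20-35%), bulbar hazard ratio k of 1.5, 2 or 3, exponential times. The spinal hazard λ per week solves s·exp(−24λk) + (1−s)·exp(−24λ) = 0.15. The treatment hazard ratio θ solves s·exp(−24λkθ) + (1−s)·exp(−24λθ) = 0.40, giving θ = 0.475, 0.459 and 0.428. The second scenario assumes θ = 0.6, which puts treated risk at about 68-71%. There were 20,000 replicates per cell, tested at two-sided 0.05.

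| Treatment effect | k | 24-week data, % power | 48-week data, % power |
|---|---|---|---|
| 85% v 60% | 1 | 94.1 v 93.9 | 97.3 v 97.2 |
| 85% v 60% | 1.5 | 94.6 v 95.0 | 97.4 v 97.6 |
| 85% v 60% | 2 | 95.0 v 96.1 | 97.4 v 98.3 |
| 85% v 60% | 3 | 95.8 v 98.1 | 98.1 v 99.4 |
| θ = 0.6 | 1 | 71.9 v 71.1 | 78.7 v 78.0 |
| θ = 0.6 | 1.5 | 70.2 v 70.8 | 77.5 v 78.6 |
| θ = 0.6 | 2 | 66.8 v 70.2 | 74.5 v 78.1 |
| θ = 0.6 | 3 | 62.1 v 71.0 | 68.8 v 77.1 |

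Over bulbar shares of 20-35% and k of 1.5-3, the gain is 0.1-2.7 points at the protocol effect and 0.5-9.7 points at θ = 0.6. The rows with k = 1 show a cost of 0.1-0.8 points when onset is not prognostic. Type I error of the stratified test was 4.8-5.3%. At two-sided 0.10, the level of the further-study rule, the gain falls to about 0-1.3 points at the protocol effect, and to about 6-8 points at θ = 0.6 with k = 3.

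The direction of the onset effect is also unknown. If bulbar onset were the slower type (k = 0.5 or 0.33), the 48-week gain would be 1.2 or 2.2 points at the protocol effect and 5.4 or 13.3 at θ = 0.6.

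**3. ALSFRS-R slope.** Using the variances in 11.1 (31.8, 0.6687, covariance 0.8527, error 2.7), a common baseline, visits at 0, 4, 12 and 24 weeks and the stated drop-out, the SE of the slope difference is 0.156 per month. Power is 80% at 2.80 × 0.156 = 0.437 per month. If onset explained 2%, 5% or 10% of slope variance (assumed), power would be 80.6%, 81.6% or 83.2%.

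**4. T-reg.** The planned model has a common baseline and unstructured covariance, so it already uses each patient's baseline value. With baseline/24-week correlation ρ and a stable onset difference explaining a fraction r of the variance, the residual variance is (1−r)[1 − ((ρ−r)/(1−r))²]. At an assumed ρ = 0.5 it is 0.750, 0.745 and 0.737 of the total for r = 0, 2% and 5%. Then d = 0.577, 0.579 and 0.583, and power is 92.7%, 92.9% and 93.1%: a gain of 0.2-0.4 points. At ρ = 0.7 it is about 0.1.

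**5. Within-onset estimates.** The 95% CI half-width is t(0.975, 2n−2) × √(2/n) SD, with n per arm. For n = 14, 21 and 25 (bulbar share 20%, 30%, 35%) it is 0.78, 0.62 and 0.57 SD. For the matching spinal n = 57, 50 and 46 it is 0.37, 0.40 and 0.41 SD. With all 71 it is 0.33 SD. The planned T-reg effect is 0.5 SD. Separate T-reg t-tests would have 25-41% power in bulbar and 66-75% in spinal patients.

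Survival is not quantified because the documents give no event rate.

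**The case against.** The strongest reply is that this is one combined document, that 4.1 is itself an analysis statement, and that nothing in 11.2 contradicts it. What is missing is a method, and a sentence would supply it. Stratified or adjusted whole-sample tests are also not the plain meaning of considering the groups separately, so the change adds something the sponsor did not promise. The benefit depends on a bulbar share and prognostic strength that are not in the documents, and the larger gains need a weaker treatment effect that is also assumed.

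Most of this stands, and it is why the point is minor. It does not remove the point, because onset is already classified under 4.1 and using it costs almost nothing.

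A reader might also infer more than the documents support.
- **That the planned tests are invalid or the trial underpowered.** Under randomisation the unadjusted tests keep their error rate, and the whole-sample power reproduces.
- **That the protocol itself shows onset predicts loss of self-sufficiency.** Inclusion criterion 5 requires "Self sufficiency: Satisfactory bulbar and spinal function (score 3+ on the ALSFRS-R for swallowing, cutting food and handling utensils, and walking", and the endpoint in 2.4 counts patients "scoring 2 or lower on at least one of the ALSFRS-R items for swallowing, cutting food and handling utensils, or walking". Both concern current function. Onset type is fixed by the first three months of symptoms, and patients enter 6 to 24 months after onset with all three items at 3 or more.
- **That T-reg power would rise by 0.7-1.8 points.** That follows from a two-sample t-test (84.1% to 84.8% or 85.9% at 2% or 5% of variance), which is not the planned model.
- **That randomisation ignored onset.** Section 6.6 names no onset stratum, but 6.5, 6.8 and most of section 7 are not shown, so nothing is claimed here.

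**Conclusion.** Minor. That 11.2 leaves the 4.1 commitment without a method is certain from the text. That stratification improves power is conditional: about 0-3 points on self-sufficiency at the protocol's effect, and about 1-10 points at an assumed hazard ratio of 0.6, for bulbar shares of 20-35% and bulbar hazard ratios of 1.5-3. Gains are smaller at the 0.1 level. If onset is not prognostic, about 1 point or less is lost. For the biomarkers, which carry the primary endpoint, the gain is probably negligible. The more durable benefit is settling before unblinding what onset-specific results may be used for.

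**What to change.** In 4.1, keep the sentence and add: *as specified in 11.2*. In 11.2, add:

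> Within each analysis set, the log-rank tests for survival and time to functional disability are stratified by onset type (bulbar or spinal, as defined in 4.1). Onset type and onset-by-time, with time coded as in the main model, are added to the ALSFRS-R, FVC and ALSAQ-40 models, and optionally to the biomarker models. Unadjusted results are reported as sensitivity analyses. Treatment estimates with 95% CIs within each onset type are descriptive and do not count toward the p<0.1 rule.

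The onset-by-time term is needed because an onset main effect alone does little for a slope contrast. Onset should be the only stratum, since crossing it with site could leave sparse cells.

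The cost is wording, plus about 1 power point or less if onset is not prognostic. No extra patients, visits or samples are needed. Table 2 lists only a general line for personal and clinical data, so the sponsor should confirm that onset type is a CRF field.

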4.2 Inclusion Criteria

- 1) Age 18 through 80 years inclusive;

- 2) Geographically accessible to the site and able to come to the site center once a week for 24 weeks;
- 3) “Definite” or “Probable” or “Probable laboratory-supported” ALS diagnosis according to the revised El Escorial criteria;
- 4) Disease duration 6 to 24 months from symptom onset to study entry;
- 5) Self sufficiency: Satisfactory bulbar and spinal function (score 3+ on the ALSFRS-R for swallowing, cutting food and handling utensils, and walking);
- 6) Satisfactory respiratory function (FVC \geq 80% of predicted);
- 7) Documented progression of symptoms in the last three months as measured by the ALSFRS-R scale (decrease of at least one point);
- 8) Ability to understand and comply with the study requirements;
- 9) Ability to give written informed consent personally or, as an alternative, via a legally authorized representative;
- 10) Treatment with riluzole 50 mg twice/day for at least 1 month prior to screening visit;

4.3 Exclusion Criteria

- 1) History of HIV, clinically significant chronic hepatitis, antecedent polio infection, or other active infection;
- 2) Motor neuron disease (MND) other than ALS;
- 3) Involvement of other systems possibly determining a functional impairment (as measured by the end-points) for the entire duration of the study;
- 4) Other severe clinical conditions (e.g., cardiovascular disorders, neoplasms) with impact on survival or functional disability in the next 12 months;
- 5) Renal insufficiency as defined by a serum creatinine $>$ 1.5 times the upper limit of normal
- 6) Poor compliance with previous treatments;
- 7) Other experimental treatments in the preceding 3 months prior to screening visit;
- 8) Women who are lactating or able to become pregnant (e.g. who are not post menopausal, surgically sterile, or using inadequate birth control) and men unable to practice contraception for the duration of the treatment and 3 months after its completion;
- 9) Unwillingness or inability to take riluzole;
- 10) Poor compliance with an inhalation device;
- 11) Abnormal liver function defined as AST and/or ALT $>$ 3 times the upper limit of the normal.

4.4 Participating Centers

Patients will be recruited by tertiary ALS centers representative of all Italian regions and by the Massachusetts General Hospital (MGH) in Boston (USA).

5. BIOMARKERS

Six candidate pharmacodynamic markers of treatment efficacy with RNS60 have been selected because they have been previously associated with ALS, they are modulated by neuroinflammation, and because some of them have been shown to be modified by RNS60 or by other compounds with anti-inflammatory properties in *in vitro* and *in vivo* models of different inflammatory conditions (see Table 1).

Table 1. Pharmacokinetic biomarkers used in this study

Type	Marker	In ALS Patients	Effect of RNS60
RNA	FoxP3 /CD25 (T-reg)	T-reg are lower in rapidly progressing ALS patients and inversely correlate with progression rates (Henkel et al., 2013).	RNS60 upregulates FoxP3 and enriches T-reg in experimental autoimmune encephalomyelitis (EAE), mouse model of multiple sclerosis (Mondal et al., 2012).
Protein	Cyp-A	Increased levels in PBMC of ALS patients and associated with disease progression (Nardo et al., 2011)	Not known
Amino acid	3-NT	Increased levels in PBMC of ALS patients (Nardo et al., 2009)	Not known, decreased by compounds with anti-inflammatory properties (Hooper et al., 2000; Yip et al., 2013)
Protein	Actin-NT	Increased levels in PBMC of ALS patients (Nardo et al., 2011)	Not known
Protein	IL17	Increased serum and CSF levels of ALS patients (Rentzos et al., 2010)	Reduced in RNS60 treated MOG and T cell transfer induced models of EAE in rats and mice (Mondal et al., 2012). Reduced in combination with IFN- γ in asthma patients after 4 weeks of treatment (Revalesio, unpublished data).
Protein	MCP1	High levels in CSF and serum of ALS patients (Kuhle et al., 2009; Baron et al., 2005).	Reduced in allergen challenge model of asthma in rats after RNS60 treatment (Ghosh et al.,

		2011).
--	--	--------

